7.2.2. Drugs That May Have Their Plasma Concentrations Altered by Ibrutinib or Venetoclax

In vitro studies indicated that ibrutinib is not a substrate of P-glycoprotein (P-gp) but is a mild inhibitor (with an IC₅₀ of 2.15 µg/mL). Ibrutinib is not expected to have systemic drug-drug interactions with P-gp substrates. However, it cannot be excluded that ibrutinib could inhibit intestinal P-gp after a therapeutic dose. There is no clinical data available; therefore, to avoid a potential interaction in the GI tract, narrow therapeutic range P-gp substrates such as digoxin, should be taken at least 6 hours before or after ibrutinib or venetoclax. If a P-gp inhibitor must be used with venetoclax, venetoclax should be dose reduced by at least 50%.

7.2.3. QT Prolonging Agents

Any medications known to cause QT prolongation should be used with caution; periodic ECG and electrolyte monitoring should be considered.

7.2.4. Antiplatelet Agents and Anticoagulants

Use ibrutinib with caution in subjects requiring anticoagulants or medications that inhibit platelet function. In an in vitro platelet function study, inhibitory effects of ibrutinib on collagen-induced platelet aggregation were observed. Supplements such as fish oil and vitamin E preparations should be avoided during treatment with ibrutinib. Bleeding events of any grade, including bruising and petechiae, occurred in subjects treated with ibrutinib. Ibrutinib should be held at least 3 to 7 days pre- and post-surgery depending upon the type of surgery and the risk of bleeding (see [Section Error! Reference source not found.](#)). Subjects with congenital bleeding diathesis have not been studied.

7.3. Prohibited Concomitant Medications

Any chemotherapy, anticancer immunotherapy, experimental therapy, or radiotherapy is prohibited while the subject is receiving ibrutinib treatment.

Corticosteroids for the treatment of the underlying disease are prohibited. Corticosteroids for the treatment of non-cancer related reasons for longer than 14 days and/or at doses >100mg of prednisone or its equivalent are prohibited.

Due to drug-drug interactions, strong CYP3A inhibitors and inducers should not be administered with venetoclax or ibrutinib. (See Appendix V).

Live-virus vaccines should not be given within 28 days prior to the initiation of study treatment, at any time during study treatment, or in the 30 days following last dose of study treatment.

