****See Section 7 regarding permissible concomitant medications, include growth factor support and CYP3A inhibitors.**

6.2.1.1. Leukocytosis/Leukostasis

A high number of circulating malignant cells (>400,000/mcL) may confer increased risk of leukostasis; these subjects should be closely monitored. Administer supportive care such as hydration and/or leukapheresis as indicated. Ibrutinib may be temporarily held, and investigator should be contacted. Venetoclax should be continued in the setting of leukocytosis/leukostasis.

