6.2.1.2. Dose Modification for Subjects with Hepatic Impairment

Subjects who develop acute hepatic toxicity with liver enzymes Grade 3 or higher while on study should be managed per standard dose modification guidelines in [Section Error! Reference source not found.](#) Ibrutinib is metabolized in the liver. In the population PK analysis (1,202 subjects), 179 subjects (14.9%) had mild hepatic impairment according to National Cancer Institute criteria and 12 subjects (1.0%) had moderate hepatic impairment. These subjects did not show a significantly higher ibrutinib exposure compared with subjects with normal hepatic function. In a hepatic impairment study, data showed an increase in ibrutinib exposure. For subjects with mild liver impairment (Child-Pugh class A), the recommended dose is 280mg daily. For subjects with moderate liver impairment (Child-Pugh class B), the recommended dose is 140mg daily. Monitor subjects for signs of ibrutinib toxicity and follow dose modification guidance as needed. It is not recommended to administer ibrutinib to subjects with severe hepatic impairment. Subjects with clinically significant chronic hepatic impairment at the time of

Screening (Child- Pugh class C) are excluded from study participation. Concomitant use of strong CYP inhibitors is not permitted in subjects with chronic hepatic impairment. Refer to Appendix D for Child-Pugh classification. Please refer to Table 3 for dose modifications due to hepatic impairment.

Table 5. Dose Modification Guidance for Hepatic Impaired Subjects

	Child Pugh class A (Mild hepatic impairment)*		Child Pugh Class B (Moderate hepatic impairment)**		Child Pugh class C (Severe hepatic impairment)
	Ongoing at time of enrollment	Develops during study	Ongoing at time of enrollment	Develops during study	Develops during study
Ibrutinib Dose (daily)	280 mg	280mg	140 mg	140 mg	Hold until improves to moderate [Class B] or better)

* If further reduction is needed due to non-hepatic toxicity, dose may be reduced to 140 mg. In the event that additional reduction is needed, ibrutinib should be held for non-hepatic toxicity until resolution.

** If further reduction is needed due to non-hepatic toxicity, ibrutinib should be held until resolution.

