7.2. Medications to be used with caution

7.2.1. CYP3A Inhibitors/Inducers

Ibrutinib is metabolized primarily by CYP3A4. Concomitant use of ibrutinib with drugs that strongly or moderately inhibit CYP3A can increase ibrutinib exposure, and strong CYP3A inhibitors should be avoided. Avoid grapefruit and Seville oranges during ibrutinib treatment as these contain moderate inhibitors of CYP3A. Dose adjustment of ibrutinib due to concomitant use of CYP3A inhibitors should follow Table 6.

Table 6. Ibrutinib Dose Modification Guidance for Co-Administration with CYP3A Inhibitors

Patient Population	Co-administered Drug	Recommended Ibrutinib Dose for the Duration of the Inhibitor Use ^a
B-Cell Malignancies	Mild CYP3A inhibitors	420 mg or 560 mg once daily per indication. No dose adjustment required.
	Moderate CYP3A inhibitors	280 mg once daily.
	Voriconazole 200mg twice daily Posaconazole suspension 100mg once daily, 100 mg twice daily, or 200 mg twice daily	140 mg once daily.
	Other strong CYP3A inhibitors Posaconazole at higher doses ^b	Avoid concomitant use and consider alternative with less CYP3A inhibitory potential. If these inhibitors will be used short-term (such as anti-infectives for seven days or less), interrupt ibrutinib. If the benefit outweighs the risk, and long-term dosing with a CYP3A inhibitor is required (more than seven days), reduce ibrutinib dose to 140 mg once daily for the duration of the inhibitor use.

^a. Monitor for adverse reactions to IMBRUVICA and interrupt or modify dose as recommended (see Dosage and Administration).

^b. Posaconazole at higher doses (posaconazole suspension 200 mg three times daily or 400 mg twice daily, posaconazole IV injection 300 mg once daily, posaconazole delayed-release tablets 300 mg once daily).

After discontinuation of a CYP3A inhibitor, resume previous dose of ibrutinib.

Avoid concomitant use of systemic strong CYP3A inducers (e.g., carbamazepine, rifampin, phenytoin, and St. John's Wort). Consider alternative agents with less CYP3A induction.

A list of common CYP3A inhibitors and inducers is provided in Appendix VI. For further information, please refer to the current version of the IB and examples of inhibitors, inducers, and substrates can be found at <http://medicine.iupui.edu/clinpharm/ddis/main-table/>. This website is continually revised and should be checked frequently for updates.

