Venetoclax should be administered using caution with weak CYP3A4 inducers and inhibitors. If a moderate CYP3A inhibitor must be used, venetoclax should be dose reduced by at least 50%. Venetoclax can be resumed at the normal dose 3 days after discontinuance of the moderate CYP3A inhibitor.

This website is continually revised and should be checked frequently for updates. For the most comprehensive effect of CYP3A inhibitors or inducers on ibrutinib exposure, please refer to the current version of the IB.

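### Section 7.3 bars strong CYP3A inhibitors with either study drug, but Table 6 gives an ibrutinib dose to use with them; nothing says which governs, and Section 7.2.1 gives no venetoclax instruction

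*Combined protocol and SAP*

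**What the plan says.** Section 7.3, under the heading for prohibited medications, states: "Due to drug-drug interactions, strong CYP3A inhibitors and inducers should not be administered with venetoclax or ibrutinib". No exception follows. Appendix VI lists voriconazole and posaconazole among the strong CYP3A inhibitors, in its prohibited part.

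Section 7.2.1 is softer. It says strong inhibitors should be avoided with ibrutinib, then sends all ibrutinib dose adjustment for CYP3A inhibitors to Table 6. Two rows of that table concern strong inhibitors:

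- The row for "Voriconazole 200mg twice daily Posaconazole suspension 100mg once daily, 100 mg twice daily, or 200 mg twice daily" gives ibrutinib 140 mg once daily.
- The row for other strong inhibitors and higher-dose posaconazole begins "Avoid concomitant use and consider alternative with less CYP3A inhibitory potential". It interrupts ibrutinib when the inhibitor is used for seven days or less. For longer use it reads "If the benefit outweighs the risk, and long-term dosing with a CYP3A inhibitor is required (more than seven days), reduce ibrutinib dose"; the reduced dose is again 140 mg a day.

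Table 6 is limited to ibrutinib by its title. The venetoclax text that follows advises caution with weak inhibitors. On moderate ones it says "If a moderate CYP3A inhibitor must be used, venetoclax should be dose reduced by at least 50" percent, with return to the normal dose 3 days after the inhibitor stops. It does not mention strong inhibitors.

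**The concern.** Every patient takes both drugs, so a strong inhibitor started on study raises two questions at once: what to do with ibrutinib, and what to do with venetoclax. On ibrutinib, 7.3 and Table 6 answer differently. On venetoclax, 7.3 says the two should not be combined, but the section a site would open for dosing instructions is silent.

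The situation is foreseeable. Section 1.5.1.5 notes fungal infections under ibrutinib and advises considering prophylaxis in patients at increased risk, and Section 7.1 allows antimicrobial prophylaxis. Exclusion 22 covers strong inhibitors at entry only, so it does not settle what happens when an azole is started later.

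At stake is patient safety and consistent conduct across three sites. Section 1.6.2.2 predicts a significant rise in venetoclax exposure when a CYP3A4 inhibitor is given with it.

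**Working it through.** The plan states no figure on this point, so the check sets the texts side by side for a patient who takes both drugs.

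| Situation | Section 7.3 | Table 6, ibrutinib | Section 7.2.1, venetoclax |
|---|---|---|---|
| Moderate inhibitor | not addressed | 280 mg | cut by at least 50%; normal dose 3 days after it stops |
| Voriconazole 200 mg twice daily, or lower-dose posaconazole | barred with both drugs | 140 mg | no instruction |
| Other strong inhibitor, default | barred with both drugs | avoid | no instruction |
| Other strong inhibitor, seven days or less | barred with both drugs | interrupt | no instruction |
| Other strong inhibitor, more than seven days, benefit outweighs risk | barred with both drugs | 140 mg | no instruction |

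**Ibrutinib.** The two strong-inhibitor rows hold four instructions. Two of them (avoid, interrupt) are compatible with 7.3. The other two give 140 mg alongside the inhibitor and are not. The 140 mg dose is a reduction of 1 − 140/420 = 67% from Dose Level 0, or 1 − 140/560 = 75% from Dose Levels 1 and 2. It is a mitigated dose, but still co-administration that 7.3 rules out.

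**Venetoclax.** With a moderate inhibitor the most a patient may take is 0.5 × 400 = 200 mg, or 0.5 × 600 = 300 mg at Dose Level 2. With a strong inhibitor, 7.2.1 gives no dose, no hold and no restart time. Even the short-term row, which stops ibrutinib, says nothing about stopping venetoclax.

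**Does any text rank the two?** Section 7.3 does not mention Table 6, and Table 6 does not mention 7.3. Section 9.1 says strong inhibitors should be avoided throughout the study, which matches the lead-in to Table 6 but does not settle precedence.

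**Cross-references.** Section 7.2.1 is right: "A list of common CYP3A inhibitors and inducers is provided in Appendix VI". Sections 7.1, 7.3 and 9.1 point instead to Appendix V, which is the medication calendar. This is clerical, and other appendix numbers in the protocol are also out of step.

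**The case against.** The strongest reply is that the stricter rule simply governs. Section 7.3 names both drugs, and Appendix VI also places strong inhibitors in its prohibited part. The lead-in to Table 6 tells the site to avoid all strong inhibitors, so the 140 mg entries can be read as a fallback for when avoidance fails. Table 6 is an ibrutinib table, and leaving venetoclax out of it is not an error in itself.

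Much of that stands. A reader might infer that the voriconazole row is unconditional permission. It is not quite that, because the avoidance sentence before the table applies to it. A reader might also infer that venetoclax has no rule for strong inhibitors. It has one, in 7.3; what is missing is an instruction in the place where dosing is set out.

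Two other texts might seem to show that the protocol means to permit strong inhibitors. The note under Table 4 says "See Section 7 regarding permissible concomitant medications, include growth factor support and CYP3A inhibitors", but it names no strength, and the mild and moderate inhibitors that Section 7.2.1 accommodates explain it fully. Section 6.2.1.2 says "Concomitant use of strong CYP inhibitors is not permitted in subjects with chronic hepatic impairment". That may be plain repetition of a bar for a higher-risk group, so it does not establish permission for everyone else.

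What the reply does not remove is that a fallback dose is still co-administration, that 7.3 allows none, and that no sentence makes the table an exception.

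**Conclusion.** The inconsistency is real and should be corrected. Sections 7.3 and 7.2.1 cannot both be followed when voriconazole or lower-dose posaconazole is given under Table 6, or when another strong inhibitor is used for more than seven days on a benefit-risk judgement. A site that relies on Table 6 is left without a venetoclax instruction in 7.2.1.

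The conclusion rests on the wording alone. The count of two conflicting instructions out of four describes the text and does not measure risk. The documents give neither an expected frequency of strong-inhibitor use nor a venetoclax exposure figure with a strong inhibitor, so no toxicity effect can be quantified. The Simon two-stage design is unaffected.

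A reader might go further and infer demonstrated harm from the raised ibrutinib exposure at Dose Level 2 (Section 5.2.1). That finding concerns 560 mg with venetoclax 600 mg, and the documents do not say how it bears on 140 mg with a strong inhibitor. Nor does comparing full-dose venetoclax with the ceiling for a moderate inhibitor show harm: it restates the 50% rule for a situation that 7.3 already forbids.

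**What to change.** Choose one rule and state it in both places.

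- **Preferred: let 7.3 govern.** Remove the two Table 6 entries that continue ibrutinib with a strong inhibitor. State in 7.2.1 that both drugs are held whenever a strong inhibitor must be given, including for seven days or less, and give a restart interval for venetoclax. The existing 3 days applies to moderate inhibitors only.
- **Alternative, if the clinical team wants to keep Table 6:** have 7.3 and Appendix VI cite it as the exception, and add a venetoclax hold to each strong-inhibitor row.

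As a clerical addition, change the Appendix V references in 7.1, 7.3 and 9.1 to Appendix VI.

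The cost is protocol wording taken through the approvals in Section 14.1, which are review and approval by the supporting company and then by the IRB. It needs no extra patients, procedures or data and no change to the statistical design.

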1.6.2.2. Toxicology

On the basis of nonclinical safety pharmacology and toxicology evaluations of venetoclax, and on the basis of nonclinical and human studies of related antiapoptotic Bcl-2 family protein inhibitors, potential mechanism-based toxicities may include lymphopenia and neutropenia, signs of tumor lysis, reduction in red cell mass, decreased spermatogenesis, skin swelling, and hair hypopigmentation. Thrombocytopenia has not been observed in toxicology studies in mice and dogs. These findings are consistent with venetoclax as a Bcl-2 specific (Bcl-XL sparing) inhibitor. Consequently, thrombocytopenia is not expected to be a dose limiting toxicity (DLT) clinically.

In vitro studies have shown that venetoclax is metabolized primarily by CYP3A4; thus, co-administration of venetoclax with drugs that inhibit CYP3A4 (such as ketoconazole) is predicted to cause a significant increase in the exposure of venetoclax and will be undertaken with caution.

For more detailed and comprehensive information regarding venetoclax, refer to the current version of the Investigator's Brochure.

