18. Any life-threatening illness, medical condition, or organ system dysfunction that, in the investigator's opinion, could compromise the subject's safety or put the study outcomes at undue risk.
19. Currently active, clinically significant cardiovascular disease, such as uncontrolled arrhythmia or Class 3 or 4 congestive heart failure as defined by the New York Heart Association Functional Classification; or a history of myocardial infarction, unstable angina, or acute coronary syndrome within 6 months prior to randomization.
20. Unable to swallow capsules or tablets or malabsorption syndrome, disease significantly affecting gastrointestinal function, or resection of the stomach or small bowel, symptomatic inflammatory bowel disease or ulcerative colitis, or partial or complete bowel obstruction.
21. Concomitant use of warfarin or other Vitamin K antagonists.
22. Subjects who received a strong cytochrome P450 (CYP) 3A inhibitor within 7 days prior to the first dose of ibrutinib or subjects who require continuous treatment with a strong CYP3A inhibitor (See Appendix VI)
23. High-grade transformation confirmed by biopsy.
24. Malabsorption syndrome or other condition precluding enteral route of administration.
25. Known CNS involvement by lymphoma

26. Erythema multiforme, toxic epidermal necrolysis, or Stevens-Johnson syndrome
27. Lactating or pregnant.
28. Unwilling or unable to participate in all required study evaluations and procedures.
29. Unable to understand the purpose and risks of the study and to provide a signed and dated informed consent form (ICF) and authorization to use protected health information (in accordance with national and local subject privacy regulations).
30. Currently active, clinically significant hepatic impairment (\geq moderate hepatic impairment according to the Child Pugh classification (class B or C)) (see Appendix X)

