APPENDIX VI DRUGS TO BE AVOIDED OR USED WITH CAUTION**PROHIBITED MEDICATIONS**

Warfarin (Coumadin)
 Biologic agents
 Anticancer therapy
 Other investigational agents
 Steroid therapy for anti-neoplastic intent

CYP3A Strong Inhibitors

Atazanavir
 Clarithromycin
 Itraconazole
 Fluvoxamine
 Nefazodone
 Nelfinavir
 Ritonavir
 Saquinavir
 Telithromycin
 Voriconazole
 Ketoconazole
 Boceprevir
 Cobicistat
 Conivaptan

Indinavir
 Lopinavir
 Mibefradil
 Posaconazole
 Telaprevir
 Troleandomycin

CYP3A Moderate Inhibitors

Fluconazole
 Aprepitant
 Erythromycin
 Diltiazem
 Verapamil
 Amprenavir
 Atazanavir
 Ciprofloxacin
 Crizotinib
 Darunavir
 Dronedaron
 Fosamprenavir
 Imatinib
 Grapefruit juice

Seville orange juice

CYP3A Strong Inducers

Avasimibe
 Carbamazepine
 Mitotane
 Modafinil
 Phenobarbital
 Phenytoin
 Rifabutin
 Rifampin
 St. John's Wort

CYP3A Moderate Inducers

Bosentan
 Efavirenz
 Etravirine
 Modafinil
 Nafcillin
 Oxcarbazepine
 Troglitazone

MEDICATIONS TO USE WITH CAUTION**CYP3A Weak Inducers**

Armodafinil
 Clobazam
 Pioglitazone
 Glucocorticoids such as prednisone
 Rufinamide
 Nevirapine
 Pioglitazone
 Vemurafenib

CYP3A Weak inhibitors

Alprazolam
 Amlodipine
 Atorvastatin
 Cimetidine
 Ranitidine
 Amiodarone
 Bicalutamide
 Cilostazol
 Cyclosporine
 Fluvoxamine
 Fluoxetine
 Ginkgo

Goldenseal
 Isoniazid
 Nilotinib
 Oral contraceptives
 Pazopanib
 Ranitidine
 Ranolazine
 Suboxone
 Tipranavir
 Ticagrelor
 Zileuton

Note that this is not an exhaustive list. Further information can be found at the following websites:

<http://medicine.iupui.edu/clinpharm/ddis/main-table/>

and

<http://www.fda.gov/Drugs/DevelopmentApprovalProcess/DevelopmentResources/DrugInteractionsLabeling/ucm080499.htm>.

APPENDIX VII LUGANO REVISED RESPONSE CRITERIA FOR NON-HODGKIN LYMPHOMA 32

Site	PET-CT- Based Response	CT-Based Response
Complete Response	Complete metabolic response	Complete radiologic response (all of the following):
Lymph nodes & extralymphatic sites	Score 1, 2, or 3 with or without a residual mass on 5-point scale	Target nodes/nodal masses must regress \leq 1.5cm in longest transverse diameter of a lesion (LDi); no extralymphatic sites of disease
Non-measured lesion	NA	Absent
Organ enlargement	NA	Regress to normal
New Lesions	None	None
Bone Marrow	No evidence of FDG-avid disease in marrow	Normal by morphology; if indeterminate, and flow cytometry IHC negative
Partial Response	Partial metabolic response	Partial remission (all of the following):

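### Section 7.3 bars strong CYP3A inhibitors with either study drug, yet Table 6 provides for some of them and no section then says how venetoclax is dosed, held or resumed

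*Combined protocol and SAP*

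**What the plan says.** **Strong inhibitors, restrictive passages.** Section 7.3 states that "strong CYP3A inhibitors and inducers should not be administered with venetoclax or ibrutinib". Exclusion 22 in Section 3.2 removes patients who received a strong inhibitor in the 7 days before the first ibrutinib dose, and also "subjects who require continuous treatment with a strong CYP3A inhibitor". Appendix VI opens under the heading "PROHIBITED MEDICATIONS", and its list of strong inhibitors, which includes voriconazole, posaconazole and ketoconazole, follows that heading.

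**Strong inhibitors, permissive passages.** Section 7.2.1 stands under the parent heading for drugs to be used with caution. Its text says "strong CYP3A inhibitors should be avoided". Table 6 then has a row beginning "Voriconazole 200mg twice daily", which also covers lower-dose posaconazole suspension. That row gives an ibrutinib dose of 140 mg once daily and no advice to avoid. The row for other strong inhibitors, and for posaconazole at higher doses, starts with avoidance. It goes on to interrupt ibrutinib for use of seven days or less and, for longer use where benefit outweighs risk, to "reduce ibrutinib dose to 140 mg once daily for the duration of the inhibitor use".

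**Venetoclax.** Section 7.2.1 asks for caution with weak inhibitors. For moderate ones it says "If a moderate CYP3A inhibitor must be used, venetoclax should be dose reduced by at least 50" per cent, with the normal dose resumed 3 days after the inhibitor stops. It has no sentence on strong inhibitors. Section 1.6.2.2 says that giving venetoclax with CYP3A4 inhibitors, with ketoconazole as the example, "is predicted to cause a significant increase in the exposure of venetoclax".

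**The concern.** Both drugs are metabolised mainly by CYP3A4, so the inhibitor rules are a safety control on exposure to each. A patient may need an azole antifungal during treatment: Section 7.1 allows antimicrobial prophylaxis, and Table 6 itself has anti-infectives in mind. One site can read Section 7.3 and decline voriconazole. Another can read Table 6 and give it with a reduced ibrutinib dose. Each is following the protocol.

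The second site then finds nothing on what to do with venetoclax, although the protocol itself predicts that venetoclax exposure will rise. Treatment runs to 24 cycles or beyond in Phase II, so the situation is not confined to the first weeks.

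**Working it through.** The point turns on no sample size, power or error rate, so the check is a comparison of text.

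**Step 1. Strong inhibitors, rule against rule.**

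| Situation in Table 6 | Section 7.3 and Appendix VI | Ibrutinib under Table 6 | Venetoclax rule beyond the Section 7.3 bar |
|---|---|---|---|
| Voriconazole 200 mg twice daily; lower-dose posaconazole suspension | Barred | 140 mg daily, no advice to avoid | None |
| Other strong inhibitors, seven days or less | Barred | Avoid; otherwise interrupt | None |
| Other strong inhibitors, more than seven days, benefit outweighs risk | Barred | Avoid; otherwise 140 mg daily | None |

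Ibrutinib is given together with a strong inhibitor in the first and third rows, which is what Section 7.3 rules out. In the second row ibrutinib is stopped, which agrees with Section 7.3 for ibrutinib but leaves venetoclax unaddressed.

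**Step 2. How uneven the instruction is.** The ibrutinib doses in the trial are 420 mg and 560 mg.
- Strong inhibitor: 140/420 = 33%, or 140/560 = 25%, of the assigned ibrutinib dose. Venetoclax: no figure.
- Moderate inhibitor: 280/420 = 67%, or 280/560 = 50%, of the assigned ibrutinib dose. Venetoclax: cut by at least half.

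The guidance covers both drugs for the moderate class and only one drug for the strong class.

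**Step 3. Does any section settle precedence?** None does, and three places read as if some use is allowed:
- The note after Table 4 sends the reader to Section 7 for permissible medications and names CYP3A inhibitors among them.
- Section 6.2.1.2 forbids strong CYP inhibitors in chronic hepatic impairment, which would be redundant under a general ban.
- Section 1.6.2.2 speaks of caution with ketoconazole as the example, while Appendix VI lists ketoconazole as a strong inhibitor.

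**Step 4. Secondary defects.**
- *Moderate inhibitors.* In Appendix VI as extracted, they come after the prohibited heading, and only weak agents follow the caution heading. Section 7.2.1 allows moderate inhibitors with changes to both drugs.
- *Fluvoxamine* is listed as strong and as weak, so it falls on both sides of the prohibited/caution line.
- *Atazanavir* is listed as strong and as moderate, which changes the Table 6 row that applies.
- *Modafinil* is listed as a strong and as a moderate inducer; both entries follow the prohibited heading.
- *Cross-references.* Sections 7.1, 7.3 and 9.1 cite Appendix V for interactions. Appendix V is the medication calendar; the drug list is Appendix VI.

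**The case against.** The best defence is that Section 7.3 controls and Table 6 is a fallback. Section 7.2.1 and the row for other strong inhibitors both lead with avoidance, Section 9.1 says the same, and short-term use leads to interruption of ibrutinib. Table 6 is titled as ibrutinib guidance, so its silence on venetoclax is to be expected. Exclusion 22 also screens out strong inhibitors at entry.

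Much of this stands, and it limits the point. A reader might infer four stronger things that the documents do not support:

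- *That there is no venetoclax instruction at all with strong inhibitors.* Section 7.3 is one, since it bars the combination. What is missing is a dose, hold or resumption rule for the situations that Table 6 tolerates.
- *That the sections are opposed throughout.* For ibrutinib, the direct conflict lies in the voriconazole and lower-dose posaconazole row and in the long-term exception.
- *That moderate inhibitors are plainly prohibited.* No sentence says so. That reading rests only on heading order in a list extracted from PDF.
- *That inhibitor use contaminated the pharmacokinetic results or lay behind the closure of Dose Level 3.* Nothing links them. Sampling was confined to Phase I, Cycle 1 Days 1, 2 and 15, exclusion 22 covers strong inhibitors before the first dose, and moderate inhibitors come with dosing rules.

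What the defence does not answer is the absence of any statement of precedence, and a Table 6 row that gives a dose with voriconazole without advising against it. Exclusion 22 works at entry; the conflict concerns inhibitors started on study.

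**Conclusion.** The inconsistency is real and should be corrected. For strong inhibitors, Section 7.3 and Appendix VI bar what Table 6 provides for. Of the three situations in Table 6, two have ibrutinib continuing with the inhibitor, and all three lack a venetoclax dose, hold or resumption rule. This rests on explicit sentences and table rows.

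The moderate-inhibitor conflict is less certain, because it depends on layout. The duplicate drug classes and wrong appendix references are plain but minor; within Appendix VI, only fluvoxamine crosses the prohibited/caution line.

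The effect on exposure or toxicity cannot be sized, because the documents give no fold-change for inhibitors and no frequency of their use. No effect on the primary response endpoint has been shown.

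**What to change.** The sponsor should reconcile Section 7.2.1 with Table 6, Section 7.3 and Appendix VI, and align Sections 1.6.2.2 and 6.2.1.2 with the result, so that:

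- each inhibitor class has one rule, and the protocol says which section governs;
- wherever a class may still be used, the handling of both ibrutinib and venetoclax is stated, including resumption;
- each drug in Appendix VI stands in one class, with fluvoxamine, atazanavir and modafinil resolved;
- the status of moderate inhibitors in Appendix VI is explicit and does not depend on heading order;
- the references in Sections 7.1, 7.3 and 9.1 point to Appendix VI.

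Which rule or dose is right is for the sponsor and its clinical advisers to decide. The cost is a protocol wording amendment; sample size, analysis and data collection do not change.
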